8.2.2. LEAP Siblings

The primary endpoint for the LEAP Siblings is the rate of peanut sensitization in younger siblings who resided in the home of the LEAP Participant on or before LEAP V60, as assessed in the current LEAP Trio study.

8.2.2.1. Computation of the Primary Endpoint

Peanut sensitization at V144 is defined as meeting at least one of the following criteria:

- a) Peanut specific IgE ≥ 0.35 kU/L
- b) Peanut specific IgE to individual peanut component Ara h2 ≥ 0.1 kU/L
- c) Skin prick test to peanut ≥ 3 mm.

LEAP Siblings who were born on or after the date of birth of the LEAP Participant will be classified as Younger Siblings. Questionnaire responses will be used to determine if the Younger Siblings resided in the home of the LEAP Participant on or before LEAP V60.

8.2.2.2. Primary Analysis: Between-group comparison

The main comparison for the LEAP Siblings is the peanut sensitization rate at V144 between the Younger Siblings of LEAP Consumers and LEAP Avoiders in the ITT population who resided in the home of the LEAP Participant on or before LEAP V60. Younger LEAP Siblings with a missing peanut sensitization status will not be included in the analyses.

This comparison will be made by a logistic regression model with a random family effect included to account for the clustering of siblings within family units and the analysis of multiple Younger Siblings. This comparison evaluates whether the Younger Siblings of the LEAP Consumers are at higher risk of peanut sensitization compared to the Younger Siblings of LEAP Avoiders due to the environmental exposure to peanut in conjunction with a lack of peanut consumption.

The same statistical methodology will be repeated for all Younger Siblings in the ITT population and in the Younger Siblings in the PP population.

The same statistical methodology will be repeated for the comparison of the peanut sensitization rate at V144 between the Older Siblings of LEAP Consumers and LEAP Avoiders in the ITT population.

8.2.2.3. Exploratory Analyses of the Primary Endpoint

Alternate definitions of peanut sensitization

Peanut sensitization at V144 will be evaluated using modifications to the definition of peanut sensitization in Section 8.2.2.1. The alternate definitions for peanut sensitization include:

1. Peanut sensitization at V144 is defined as meeting at least one of the following criteria:
 - a. Peanut specific IgE to individual peanut component Ara h2 ≥ 0.1 kU/L
 - b. Peanut specific IgE to individual peanut component Ara h6 ≥ 0.1 kU/L
2. Peanut sensitization at V144 is defined as meeting at least one of the following criteria:
 - a. Meeting the criteria in alternate peanut sensitization definition #1
 - b. Skin prick test to peanut ≥ 3 mm

The prevalence of peanut sensitization using alternate definition #1 will be compared between Younger Siblings of LEAP Consumers and LEAP Avoiders in the ITT population using a logistic regression model with a random family effect included to account for the clustering of siblings within family units and the analysis of multiple Younger Siblings.

The same statistical methodology will be repeated for Younger Siblings in the PP population.

The same statistical methodology will be repeated for Older Siblings in the ITT population.

The above exploratory analyses in the Younger Siblings and Older Siblings will be repeated for the prevalence of peanut sensitization using alternate definition #2. The prevalence of peanut sensitization for peanut specific IgE to each of the individual peanut components (Ara h1, Ara h2, Ara h3, Ara h6, Ara h8) will be analyzed separately for each peanut component, with sensitization defined as peanut specific IgE to individual peanut component ≥ 0.1 kU/L. The prevalence of peanut sensitization for each peanut component will be compared between the

Younger Siblings of LEAP Consumers and LEAP Avoiders in the ITT population using a logistic regression model with a random family effect included to account for the clustering of siblings within family units and the analysis of multiple Younger Siblings.

The same statistical methodology will be repeated for the prevalence of peanut sensitization for peanut specific IgE to each of the individual peanut components (Ara h1, Ara h2, Ara h3, Ara h6, Ara h8), separately, in Older Siblings in the ITT population.

Factors affecting peanut sensitization

The peanut sensitization status of LEAP Trio Siblings in the ITT populations will be analyzed using logistic regression models with a random family effect and possible fixed effects including treatment arm, whether Younger or Older sibling, age at V144, TEWL measurement, sibling history of eczema, whether resided in home of LEAP Participant on or before V60, peanut protein in bed dust at V144, peanut protein in bed dust of LEAP Participant at V60, peanut consumption of the sibling during the first year of life, and peanut consumption of LEAP Participant during the LEAP study. The fixed effects, along with possible interactions terms, will be evaluated for inclusion in the final logistic regression model.

8.3. Secondary Endpoints

8.3.1. LEAP Participants, Siblings, and Parents: Clinical

For a listing and numbering of the secondary endpoints, see the Protocol Summary in Section 3 above and Section 3.2.2 of the protocol V7.0. Analyses of the secondary endpoints are summarized in Table 8.3.1 below. Details of the secondary endpoint analyses are provided in sections 8.3.2 through 8.3.10.

Table 2: Overview of Analyses of the Secondary Clinical Endpoints

Secondary Endpoint	LEAP Participant Analysis	LEAP Sibling Analysis	LEAP Parent Analysis
Clinical 1,2,3,4*	The amount of peanut consumption, SCORAD, skin-prick test wheal sizes, and specific-IgE measurements including IgE to Ara h2 and other components will be compared between LEAP avoiders and LEAP consumers using parametric and non-parametric tests (e.g. Wilcoxon and t-test). The data will first be tested to determine normality. If the data are not normal then a Wilcoxon test will be run. If the data are normal then tests will be run to determine if the variances are equal between the two groups. If the variances are equal, a two sample t-test assuming equal variances will	The amount of peanut consumption, SCORAD, skin-prick test wheal sizes, and specific-IgE measurements including IgE to Ara h2 and other components will be compared between the siblings of the LEAP avoiders and LEAP consumers using linear mixed effects models with a random family effect included to account for the clustering of siblings within family units and the analysis of multiple siblings.	The amount of peanut consumption, skin-prick test wheal sizes, and specific-IgE measurements will be compared between the parents of the LEAP avoiders and LEAP consumers using linear mixed effects models with a random family effect included to account for the clustering of parents within family units.

Secondary Endpoint	LEAP Participant Analysis	LEAP Sibling Analysis	LEAP Parent Analysis
	be used; otherwise, a two sample t-test assuming unequal variances will be used.		
5,6 ⁺	The prevalence of asthma, rhinitis and eczema will be compared between LEAP avoiders and LEAP consumers using a two-tailed, chi-squared test at the 0.05 level of significance.	The prevalence of asthma, rhinitis, and eczema will be compared between the siblings of the LEAP avoiders and LEAP consumers using a logistic regression model with a random family effect included to account for the clustering of siblings within family units and the analysis of multiple siblings.	The prevalence of asthma, rhinitis, and eczema will be compared between the parents of the LEAP avoiders and LEAP consumers using a logistic regression model with a random family effect included to account for the clustering of parents within family units.
7		The proportion of participants with peanut allergy will be compared between the siblings of the LEAP avoiders and LEAP consumers using a logistic regression model with a random family effect included to account for the clustering of siblings within family units and the analysis of multiple siblings.	The proportion of participants with peanut allergy will be compared between the parents of the LEAP avoiders and LEAP consumers using a logistic regression model with a random family effect included to account for the clustering of parents within family units.
8	The proportion of participants experiencing at least one peanut-related adverse event will be compared between LEAP avoiders and LEAP consumers using a logistic regression model.	The proportion of participants experiencing at least one peanut-related adverse event will be compared between the siblings of the LEAP avoiders and LEAP consumers using a logistic regression model with a random family effect included to account for the clustering of siblings within family units and the analysis of multiple siblings.	

*Secondary clinical endpoint #4 is only collected in LEAP participants and siblings of LEAP participants.

+Secondary clinical endpoint #6 is only collected in the parents of LEAP participants.

8.3.2. Secondary Endpoint 1: Peanut consumption

Peanut consumption questionnaires will be used to determine the amount of each participant's average weekly peanut protein consumption in the 4 weeks prior to V144 for participants in all 4 cohorts (LEAP Participants, Older Siblings, Younger Siblings, and Parents). For LEAP Participants, the peanut consumption questionnaires will also be used to determine the amount of each LEAP Participant's average weekly peanut protein consumption in the 4 weeks immediately following the final LEAP or LEAP-On study visit, the longest period during which

the participant stopped eating peanut and yearly peanut consumption metrics since the final LEAP or LEAP-On study visit.

8.3.2.1. LEAP Participants

The average weekly peanut protein consumption prior to V144 for the LEAP Participants in the ITT population will be compared between LEAP Consumers and LEAP Avoiders using the most appropriate parametric or non-parametric tests (e.g. Wilcoxon and t-test) for the peanut consumption data. The data will first be tested to determine normality. If the data are not normal then a Wilcoxon test will be run. If the data are normal then tests will be run to determine if the variances are equal between the two groups. If the variances are equal, a two sample t-test assuming equal variances will be used; otherwise, a two sample t-test assuming unequal variances will be used.

The same statistical methodology will be repeated in the average weekly peanut consumption immediately following LEAP or LEAP-On for the LEAP Participants in the ITT population.

8.3.2.1.1. Exploratory Analyses of Peanut Consumption

Average period not eating peanut in years following LEAP and LEAP-On

The average of the longest period in months during which the LEAP Participants in the ITT population stopped eating peanut or were not eating peanut since their final LEAP or LEAP-On study visit will be compared between LEAP Consumers and LEAP Avoiders using the most appropriate parametric or non-parametric tests (e.g. Wilcoxon and t-test) for the peanut consumption data. The data will first be tested to determine normality. If the data are not normal then a Wilcoxon test will be run. If the data are normal then tests will be run to determine if the variances are equal between the two groups. If the variances are equal, a two sample t-test assuming equal variances will be used; otherwise, a two sample t-test assuming unequal variances will be used.

Average yearly peanut consumption in years following LEAP and LEAP-On

The average yearly peanut consumption per year for up to 7 years since the final LEAP or LEAP-On study visit may be presented graphically by treatment arm to identify trends in peanut consumption over time for additional analyses.

8.3.2.2. LEAP Siblings and Parents

The average weekly peanut protein consumption prior to V144 for the LEAP Siblings in the ITT population will be compared between LEAP Consumers and LEAP Avoiders using a linear mixed effects model with a random family effect included to account for the clustering of siblings within family units and the analysis of multiple siblings. Older Siblings and Younger Siblings will be analyzed separately.

The same statistical methodology will be repeated for the LEAP Parents in the ITT population.

8.3.3. Secondary Endpoint 2: Skin prick test

Skin prick tests will be performed at V144 on participants in all 4 cohorts (LEAP Participants, Older Siblings, Younger Siblings and Parents) to assess sensitivity to peanut, other select foods, and select aeroallergens.

8.3.3.1. LEAP Participants

The peanut skin prick test wheal size (mm) for the LEAP Participants in the ITT population will be compared between LEAP Consumers and LEAP Avoiders using the most appropriate parametric or non-parametric tests (e.g. Wilcoxon and t-test) for the skin prick test data. The data will first be tested to determine normality. If the data are not normal then a Wilcoxon test will be run. If the data are normal then tests will be run to determine if the variances are equal between the two groups. If the variances are equal, a two sample t-test assuming equal variances will be used; otherwise, a two sample t-test assuming unequal variances will be used.

The same statistical methodology will be repeated on skin prick test wheal size measurements for all tested allergens.

8.3.3.2. LEAP Siblings and Parents

The peanut skin prick test wheal size (mm) for the LEAP Siblings in the ITT population will be compared between LEAP Consumers and LEAP Avoiders using a linear mixed effects model with a random family effect included to account for the clustering of siblings within family units and the analysis of multiple siblings. Older Siblings and Younger Siblings will be analyzed separately.

The same statistical methodology will be repeated on skin prick test wheal size measurements for all tested allergens.

The same statistical methodology will also be repeated for the LEAP Parents in the ITT population on all tested allergens.

8.3.4. Secondary Endpoint 3: Immunoglobulin measurements

Blood samples will be collected at V144 and analyzed for immunoglobulin levels from participants in all 4 cohorts (LEAP Participants, Older Siblings, Younger Siblings, and Parents) to assess IgE levels, a continuous measure, to peanut, other select foods, and select aeroallergens. The blood samples at V144 will also be analyzed for levels of peanut IgG, peanut IgG4, and components to peanut IgE and peanut IgG4.

8.3.4.1. LEAP Participants

The peanut specific IgE measurements (kU/L) for the LEAP Participants in the ITT population will be compared between LEAP Consumers and LEAP Avoiders using the most appropriate parametric or non-parametric tests (e.g. Wilcoxon and t-test) for the data. The measurements will be log-transformed for analysis. The log-transformed data will first be tested to determine normality. If the data are not normal then a Wilcoxon test will be run. If the data are normal then tests will be run to determine if the variances are equal between the two groups. If the variances are equal, a two sample t-test assuming equal variances will be used; otherwise, a two sample t-test assuming unequal variances will be used.

The same statistical methodology will be repeated on the immunoglobulin measurements for all tested items, as well as IgG4/IgE ratio.

Longitudinal analyses with LEAP and LEAP On

The immunoglobulin measurements at V144 for LEAP Participants will be linked with the participants' immunoglobulin measurements obtained at visits V-1 (Screening), V12, V30, and V60 from the LEAP study and with the immunoglobulin measurements obtained at V72 from the LEAP-On study. Select immunoglobulins will be compared between LEAP Consumers and LEAP Avoiders, as well as between visits, and will be presented graphically. Select immunoglobulins may also be compared between LEAP Consumers and LEAP Avoiders across the visits using extreme value theory methods to test the differences in the upper quantiles.

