# 9.3 SAMPLE SIZE

# **LEAP Participants**

The sample size is based on the number of children likely to be available to enroll in the study. As shown in the Figure 1 LEAP Screening, Participant and Sibling Cohorts, there are 311 LEAP avoiders and 319 LEAP consumers (total 630) potentially eligible for enrollment. In the LEAP study, the rate of peanut allergy was 3.2% among consumers and 17.2% among avoiders at 60 months of age. We assume that the rates will not change markedly between month 60 and 144. We wish to detect a difference between the groups that are similar to that detected at 60 months. 88.5% of those potentially eligible enrolled in the follow on LEAP-On Study. We assume a lower percentage of those potentially eligible will enroll in this study.

For example, if 80% of those potentially eligible enroll, the true rate of allergy among LEAP consumers at 144 months is 6%, and the true rate of allergy among LEAP avoiders at 144 months is 15%, there is 91% power to detect a difference with a two-sided type I error of 0.05 between the groups. If only 70% enroll and other assumptions remain constant, there would be about 87% power to detect a difference.

Other examples are shown in Figure 3.

Three possible recruitment rates are shown in the left, middle and right panels. In each panel, the power to detect a difference, with a two-sided type I error of 0.05, between groups is shown on the vertical axis for different assumptions regarding the true underlying allergy rates in the consumer and avoider groups at month 144. In each panel contour lines display rates in consumers of 2%, 4%, 6%, 8% and 10% while the horizontal axis displays a range of rates in avoiders of 10 to 25%

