6.2. Demographic and Other Baseline Characteristics

Summary descriptive statistics for demographic characteristics collected at Visit 144 will be reported for the enrolled, ITT and PP samples by LEAP Trio participant cohort and treatment arm. Characteristics to be summarized include age, ethnicity, and sex.

Summary descriptive statistics for demographic, baseline, V60 characteristics collected in LEAP, and V72 characteristics collected in LEAP On will be presented by treatment arm for participants who did and did not participate in the LEAP Trio study. Characteristics to be presented include age, ethnicity, sex, skin prick test to peanut, and peanut IgE and its components.

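### The V144 comparisons of peanut wheal and immunoglobulins in LEAP participants ignore baseline values already held, and so give up some precision

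*SAP*

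**What the plan says.** SAP 8.3.4.1 (immunoglobulins, LEAP participants): "The peanut specific IgE measurements (kU/L) for the LEAP Participants in the ITT population will be compared between LEAP Consumers and LEAP Avoiders". Values are log-transformed and tested for normality. A Wilcoxon test follows if normality fails. Otherwise a two-sample t-test is used, with the variance assumption chosen by a further test. The scheme is repeated for the other immunoglobulins and the IgG4/IgE ratio.

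SAP 8.3.3.1 (skin prick test): "The peanut skin prick test wheal size (mm) for the LEAP Participants in the ITT population will be compared between LEAP Consumers and LEAP Avoiders", by the same scheme on the millimetre scale. Neither comparison has a covariate. Protocol 9.2.2 names the same tests.

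Three items show what is held from before randomisation:

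- SAP 8.3.4.1, longitudinal paragraph: V144 immunoglobulins are linked to "measurements obtained at visits V-1 (Screening), V12, V30, and V60 from the LEAP study".
- SAP 6.2: LEAP baseline data are tabulated by arm for children who did and did not join LEAP Trio. "Characteristics to be presented include age, ethnicity, sex, skin prick test to peanut, and peanut IgE and its components".
- SAP 8.2.1.2: the LEAP randomisation was stratified by SPT result (positive or negative). The stratum is used to split the primary allergy analysis, but not for wheal or IgE.

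The longitudinal paragraph also plans comparisons of selected immunoglobulins between arms and visits, plots, and an optional upper-quantile method. It names no model and does not mention wheal size.

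**The concern.** A pre-randomisation measurement of the outcome itself is usually among the better predictors available. If infant sensitization still predicts wheal or IgE at about age 12, leaving it out puts explainable variation into the error term and widens the interval for the arm effect.

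The SAP uses covariate models elsewhere: supplementary models for the primary allergy endpoint (8.2.1.2), TEWL (8.4.4.1) and lung function (10.1.1). Wheal and IgE in participants, where the same measure exists from before randomisation, have no such analysis.

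What is at stake is the precision of two secondary endpoints, and protection against any imbalance in measured baseline sensitization among the children who return.

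**Working it through.** **1. Inputs.** Protocol 9.3 says "there are 311 LEAP avoiders and 319 LEAP consumers (total 630) potentially eligible for enrollment". It works an example "if 80% of those potentially eligible enroll", which gives 0.8 × 311 = 248.8 avoiders and 0.8 × 319 = 255.2 consumers, 504 in all. Its allergy rates are 15% (avoiders) and 6% (consumers), with two-sided alpha 0.05. The documents state no power for wheal or IgE and no correlation between screening and V144 values. Rho is therefore an assumption, shown as a range.

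**2. The plan's own figure.** Pooled-variance normal approximation for two proportions:

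- Pooled rate = (248.8 × 0.15 + 255.2 × 0.06) / 504 = 0.1044.
- Null SE = √[0.1044 × 0.8956 × (1/248.8 + 1/255.2)] = 0.02725.
- Alternative SE = √[0.15 × 0.85/248.8 + 0.06 × 0.94/255.2] = 0.02708.
- Power = Φ[(0.09 − 1.96 × 0.02725)/0.02708] = Φ(1.35) = 91.2%, against 91% stated.
- At 70% enrolment the same steps give 87.2%, against about 87% stated.

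The plan's figures reproduce, so these sample sizes are used below.

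**3. What adjustment buys with roughly normal data.** Residual variance falls by the factor 1 − rho². The interval narrows by 1 − √(1 − rho²). Adjusted power = Φ[(1.96 + z)/√(1 − rho²) − 1.96], where z is the normal quantile of the unadjusted power. For 80% power, z = 0.8416. At N = 504 this corresponds to a difference of 2.8016 × √(1/248.8 + 1/255.2) = 2.8016 × 0.0891 = 0.25 SD.

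| rho (assumed) | 1 − rho² | CI narrower by | 80% power becomes |
|---|---|---|---|
| 0.1 | 0.99 | 0.5% | 80.4% |
| 0.2 | 0.96 | 2.0% | 81.6% |
| 0.3 | 0.91 | 4.6% | 83.6% |
| 0.4 | 0.84 | 8.3% | 86.4% |
| 0.5 | 0.75 | 13.4% | 89.9% |

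From 90% unadjusted power, the same formula gives 92.5% at rho 0.3 and 96.3% at rho 0.5. From 95% it gives 98.6% at rho 0.5, a gain of under 4 points.

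**4. What happens with values at a floor.** Many wheals may be zero and many IgE values may sit at the detection limit. A simulation used 249 v 255 children, a 0.25 SD difference and 2,000 runs per setting. Baseline and outcome were bivariate normal, and both were cut off at a floor. The floor shares are assumptions and refer to the outcome in the unshifted arm; rho is the correlation before the cut-off. The SPT stratum was not modelled. Power in %:

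| At floor | rho | t-test | Wilcoxon | ANCOVA | Rank ANCOVA |
|---|---|---|---|---|---|
| none | 0.2 | 78.6 | 77.5 | 80.1 | 78.9 |
| none | 0.4 | 79.0 | 77.0 | 86.2 | 83.5 |
| none | 0.6 | 79.8 | 78.0 | 93.3 | 91.5 |
| about 50% | 0.2 | 68.2 | 71.7 | 68.8 | 72.5 |
| about 50% | 0.4 | 67.5 | 71.1 | 74.4 | 76.3 |
| about 50% | 0.6 | 68.5 | 71.7 | 81.9 | 82.9 |
| about 80% | 0.2 | 48.1 | 55.1 | 48.8 | 55.8 |
| about 80% | 0.4 | 48.7 | 56.0 | 50.6 | 57.9 |
| about 80% | 0.6 | 46.2 | 54.3 | 55.1 | 63.6 |

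Like for like (ANCOVA against t, rank ANCOVA against Wilcoxon), adjustment was never worse, and type I error stayed at about 4% to 6%. Plain ANCOVA, however, fell below the planned Wilcoxon in three settings: about 50% at the floor with rho 0.2, and about 80% at the floor with rho 0.2 or 0.4.

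**The case against.** The planned tests are valid. The arms were randomised, and the test's type I error already covers chance imbalance. A reader might infer that the unadjusted comparison is biased, but the documents do not support that. SAP 6.2 will examine whether returning children differ from the others, and nothing shows that a differential imbalance is expected. This objection stands.

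Rho may be small. Protocol 3.1 implies a gap from LEAP entry to V144 of about 9 years (minimum age 9.5 years less entry at 4.5 months) up to 15.6 years (5,689 days). Ara h2 IgE fell in the consumption arm (Protocol 1.2), and telephone visits accept outside results or home-collected blood (Protocol 6.2.3). All of these could weaken the correlation. A reader might take rho 0.5, which is equivalent to 504/0.75 = 672 children or a third more, as the expected gain. No source in the documents supports that value.

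Base power may already be high for key analytes. Ara h2 IgE, IgG4 and the IgG4:IgE ratio differed between arms at p<0.001 at both 60 and 72 months (Protocol 1.2), and there the gain would be small.

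A reader might also infer that adjustment is free. It is not: a linear model can lose power to the planned Wilcoxon when values pile up at a floor, and missing baselines need a rule.

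Two further objections carry less weight. The longitudinal paragraph of SAP 8.3.4.1 does use screening immunoglobulins, but it specifies no model and leaves out wheal, so it yields no baseline-adjusted V144 estimate. Protocol 7.2.1 considers retesting stored plasma optimal for quantitative comparison across studies. A covariate, though, needs only to predict the outcome within arms, so assay drift may lower rho without invalidating the adjustment.

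**Conclusion.** The point holds as a modest matter of efficiency. Two secondary comparisons leave out baseline information already in hand, and no other part of the plan supplies the adjusted estimate.

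The size rests on an assumed rho. Over 0.2 to 0.5 the interval is about 2% to 13% narrower, and 80% power rises to between 82% and 90%. At rho of 0.1 to 0.2 the gain is negligible. It also shrinks where power is already high or most values sit at the floor: with about 80% there and rho 0.2, rank ANCOVA gained less than one point over Wilcoxon.

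The planned tests need not be called wrong, and the co-primary analyses are unaffected.

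**What to change.** In SAP 8.3.3.1 (peanut wheal) and 8.3.4.1 (each immunoglobulin with a screening value):

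- Pre-specify as the between-arm test a rank ANCOVA of the V144 value on arm, baseline value and SPT randomisation stratum. Use only pre-randomisation values as covariates, not V12 to V72.
- For immunoglobulins only, use linear regression of log V144 value on arm, log screening value and stratum, reporting the ratio of geometric means with 95% CI, where the share of values at the detection limit is below a threshold fixed in advance. Assess that share blinded to arm.
- Keep the unadjusted test as supportive, and as the main test for analytes or allergens without a baseline.
- State a rule for missing baselines, for example a missing indicator.

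The cost is some analysis work and document changes, with no new data collection. The change should be recorded in SAP section 11. The tests named in Protocol 9.2.2 must be aligned. If the change counts as a principal feature, Protocol 9.5 requires an amendment subject to DSMB, sponsor and Ethics Committee review.
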